## Operationalization of Variables

### Independent Variable:

- Treatment: Administration of the study drug versus placebo (categorical variable with two levels: active treatment or placebo).

Dependent Variables (Primary Outcomes):

- Development of gastrointestinal infections — categorical nominal binary variable (yes/no)
- Development of upper respiratory infections — categorical nominal binary variable (yes/no)
- Development of lower respiratory infections — categorical nominal binary variable (yes/no)
- Development of urinary tract infections — categorical nominal binary variable (yes/no)
- Development of soft tissue infections — categorical nominal binary variable (yes/no)
- Rehospitalization due to infection — categorical nominal binary variable (yes/no)
- Development of septic shock — categorical nominal binary variable (yes/no)
- Requirement for long-term renal replacement therapy — categorical nominal binary variable (yes/no)
- Death from any cause — categorical nominal binary variable (yes/no)
- Progression to chronic kidney disease or  $\geq 50\%$  decline in eGFR — categorical nominal binary variable (yes/no)
- Worsening renal function with  $\geq 25\%$  decline in eGFR due to infection — categorical nominal binary variable (yes/no)
- Presence of hyperkalemia — categorical nominal binary variable (yes/no)
- Adverse drug reactions — categorical nominal variable

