### Research Question:

Does administration of trimethoprim-sulfamethoxazole 800/160 mg every 48 hours for 90 days reduce the risk of infections in patients who have experienced severe acute kidney injury after hospital discharge?

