### Study Objectives

#### Primary Objective:

To reduce the risk of infections within 90 days following hospital discharge after a severe episode of acute kidney injury (AKI).

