#### Secondary Objectives:

To evaluate the risk of rehospitalization, infection-related rehospitalization, septic shock, major adverse kidney events (MAKE) at 90 days, incidence of hyperkalemia, and new episodes of acute kidney injury. Adverse events (AEs) will be coded using the Medical Dictionary for Regulatory Activities (MedDRA) and classified as mild, moderate, or severe. AEs of special interest include skin rash, erythema, nausea, vomiting, headache, and tachycardia.

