### Working Hypothesis

Hypothesis: Administration of trimethoprim–sulfamethoxazole 800/160 mg every 48 hours for 90 days reduces the risk of infections.

Null Hypothesis: Administration of trimethoprim–sulfamethoxazole 800/160 mg every 48 hours for 90 days does not reduce the risk of infections.

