### Materials and Methods

- This study will be a phase 2, randomized, prospective, double-blind, investigator-initiated, parallel-group, placebo-controlled clinical trial conducted at the Hospital Civil de Guadalajara “Fray Antonio Alcalde”, Guadalajara, Mexico. All patients with AKI receiving nephrology consultation will be considered for inclusion.
- The diagnosis of AKI will follow the Kidney Disease: Improving Global Outcomes (KDIGO) serum creatinine criteria. In accordance with the recommendations of the 31st Acute Disease Quality Initiative Group regarding the design of clinical trials for AKI treatments, the subphenotype of patients at the highest risk of post-AKI infections will be selected. This study will be considered a phase 2 randomized, double-blind, placebo-controlled trial meeting efficacy (AKI trajectory and eGFR evaluation), feasibility (patient recruitment and protocol adherence), and safety (adverse events and drug reactions) objectives.
- Group randomization will be performed using the clinical trial randomization tool available at <http://www.winepi.net/f108.php>, employing traditional block randomization. Sequences for each arm and stratum will be generated using maximal asymptotic randomization.
- Patients will be recruited on an outpatient basis to document any infectious event of any kind occurring within the first 90 days, as well as cases of rehospitalization due to infection within the same period at the Hospital Civil de Guadalajara “Fray Antonio Alcalde”.

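### The only list of primary outcomes names 13 variables, leaves out infection overall, and includes three outcomes the protocol elsewhere makes secondary

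*Protocol*

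**What the plan says.** Three sections of the protocol pose the same question. Research Question asks whether the drug will "reduce the risk of infections in patients who have experienced severe acute kidney injury after hospital discharge". Primary Objective sets the window: "To reduce the risk of infections within 90 days following hospital discharge after a severe episode of acute kidney injury (AKI". Working Hypothesis says that treatment "every 48 hours for 90 days reduces the risk of infections".

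Secondary Objectives then lists any rehospitalization, "infection-related rehospitalization, septic shock, major adverse kidney events (MAKE) at 90 days, incidence of hyperkalemia", "and new episodes of acute kidney injury". Adverse events are described in the same section.

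Operationalization of Variables holds the only list labelled primary, under the heading "Dependent Variables (Primary Outcomes". Its 13 entries are:
- five infection sites: gastrointestinal, upper respiratory, lower respiratory, urinary tract and soft tissue;
- rehospitalization for infection, and septic shock;
- long-term renal replacement therapy, death, progression to CKD or an eGFR fall of at least 50%, and an eGFR fall of at least 25% due to infection;
- hyperkalemia, and adverse drug reactions.

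Materials and Methods plans to "document any infectious event of any kind occurring within the first 90 days", without calling this primary. The same section describes the trial's efficacy aim as "efficacy (AKI trajectory and eGFR evaluation"), with no mention of infection. Statistical Analysis refers to primary and secondary outcomes without saying which is which. It applies a two-sided 0.05 threshold to every test and states no adjustment.

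**The concern.** The protocol intends a hierarchy, since it has a primary objective, secondary objectives and an analysis section that refers to both classes. The one list that should turn this hierarchy into variables does not follow it. The comparison that the primary objective calls for is not a defined variable, and some outcomes are labelled both primary and secondary.

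Read literally, the list allows any of 13 results to be reported as a primary finding. A benefit on one infection site or one kidney item could be presented as a primary success even if infection overall was not reduced. A statistical analysis plan cannot settle this by adding detail. Whatever it chose, it would contradict one section of the protocol.

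**Working it through.** **1. The lists side by side**

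| Item | Objectives sections | List of primary outcomes |
|---|---|---|
| Infection of any site, 90 days | Primary | Absent |
| Five separate infection sites | Not listed separately | Primary |
| Rehospitalization for infection | Secondary | Primary |
| Septic shock | Secondary | Primary |
| Hyperkalemia | Secondary | Primary |
| Any rehospitalization | Secondary | Absent |
| New AKI episodes | Secondary | Absent |
| MAKE at 90 days | Secondary | Absent by name |

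The count is 13 entries, none for overall infection, and three explicit conflicts. Three is the conservative number. Renal replacement therapy, death and the CKD/eGFR item look like parts of MAKE, but the protocol does not define MAKE, so they are not counted.

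The five sites cannot be assumed to add up to any infection. No section says they form a composite. Background reports abdominal infections as 9% of infections in the Spanish cohort, and it is unclear whether the gastrointestinal entry covers them. Bloodstream infection has no entry.

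Presentation of Information does not fill the gap. It plans a table of reported infections and a Kaplan–Meier curve whose event is not named.

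**2. The protocol's own sample size**

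Inputs from Sample Size: 59% versus 29.5%, 95% confidence, 90% power, 60 per group.

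Pooled formula, with mean proportion 0.4425 and difference 0.295:
- null term: 1.960 × √(2 × 0.4425 × 0.5575) = 1.3767
- alternative SD: √(0.59 × 0.41 + 0.295 × 0.705) = 0.6707
- n = (1.3767 + 1.2816 × 0.6707)² / 0.295² = 57.5, so 58 per group, close to the stated 60
- power at 60: Φ[(0.295 × √60 − 1.3767) / 0.6707] = Φ(1.354) = 91.2%

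Exact enumeration at 60 per group gives 91.6% for the uncorrected chi-square test and 88.3% for Fisher's exact test. The stated size therefore fits one comparison of proportions at 0.05.

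**3. Chance of a false primary benefit**

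Take the 11 entries other than hyperkalemia and adverse drug reactions. Count only false results in favour of treatment, at 0.025 each.

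| Assumption | At least one false benefit |
|---|---|
| Independent: 1 − 0.975¹¹ | 24.3% |
| Equicorrelated normal, 0.2 | 20.9% |
| Equicorrelated normal, 0.5 | 15.2% |
| All event rates 10%, independent | 11.3–22.5% |
| All event rates 5%, independent | 5.6–7.9% |
| One primary outcome | 2.5% |

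The last two multi-item rows use exact enumeration with 60 per arm. The lower figure uses Fisher's test throughout (size per item 0.0109 at 10%, 0.0053 at 5%). The upper figure uses Fisher only when an expected count is below 5 (0.0229 and 0.0074). The correlations and event rates are assumptions, because the protocol gives none for these items.

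Counting either direction over all 13 entries, with adverse drug reactions treated as one test, gives 1 − 0.95¹³ = 48.7% if independent and 33.4% at correlation 0.5. With 5% event rates it is 12.8–17.7%.

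**4. Keeping all 13 with an adjustment**

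Bonferroni gives 0.05/13 = 0.00385 per test. Even if every outcome had the 59% versus 29.5% rates, 60 per group would give 64.8% power, and 90% power would need 96 per group.

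**The case against.** The strongest reply is that this is a mislabelled list, not 13 intended primary outcomes. The heading begins with dependent variables, the entries include adverse drug reactions, three sections name infection as the question, and the sample size uses one pair of proportions. That reading is plausible and narrows the practical risk. But it does not supply the missing infection variable or remove the conflict with Secondary Objectives. If the list is meant to hold every outcome, any rehospitalization and new AKI episodes are missing from it as well.

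A second reply is that 24% is a worst case. This is fair. Some items require an infection, so they are not independent, and many events will be rare at 60 per arm. An alternative calculation applies the site shares in Background (urinary 44%, respiratory 30% split equally, soft tissue 9%, abdominal 9% standing for gastrointestinal) to overall infection of 30%, 42% or 59%. With the other six items at 5% and all independent, it gives 5–8% with Fisher and 8–12% with the mixed rule. Those figures are well below 24% but still at least twice 2.5%.

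Third, the power statement holds only for 59% versus 29.5%. Sample Size also says that about 30% of patients will have an infection. At 30% versus an assumed 15%, exact power at 60 per group is 42% (Fisher) to 51% (chi-square). This is a real conflict within that section, but a separate one, and it does not affect which outcome should be primary.

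Finally, naming the exact test can be left to the statistical analysis plan. That is accepted, and the point does not depend on it.

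**Conclusion.** The concern holds, and the protocol must be corrected. The primary objective has no matching primary outcome, and three outcomes are classed both as primary and as secondary. These are facts of the text and rest on no assumption.

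The size of the false-positive risk does depend on assumptions. It runs from about 5–8% when events are rare to 24% with independent tests at nominal size, against at most 2.5% for one primary outcome. The lower part of that range is the more realistic for 60 per arm if most listed events are uncommon. The case for correction does not rest on the upper figure.

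**What to change.** In Operationalization of Variables, name one primary outcome: at least one infection of any site within 90 days of hospital discharge (yes/no), with one pre-stated primary test at two-sided 0.05. Comparing two proportions matches the sample size calculation, with log-rank on time to first infection as supportive. Log-rank as the primary test would also be defensible, but only one can be primary. Stating the exact test in the protocol is desirable but optional.

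Move the five sites, infection rehospitalization, septic shock, and the kidney and death items to secondary outcomes. Move hyperkalemia and adverse drug reactions to safety. Add variables for any rehospitalization and new AKI episodes, and say which items make up MAKE. Then align Secondary Objectives, the efficacy statement in Materials and Methods, and Statistical Analysis with the new list.

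This should be done before outcome data are seen. It changes wording only, because Materials and Methods already plans to record every infectious event over 90 days, so no visit or measurement is added. A working definition of infection will be needed, and because data are extracted from the institutional record, infections treated elsewhere may be missed; both apply equally to the present list. The price is that the other outcomes can no longer support a claim on their own, and the log-rank result becomes supportive.

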## Data Collection and Observation Techniques

Data will be collected through automated extraction from the institutional electronic medical record system. Additional potential contributors to AKI—such as nephrotoxic medications (aminoglycosides, nonsteroidal anti-inflammatory drugs, and vancomycin)—will also be considered.

The presence of anaphylactic shock will be documented, and relevant biochemical parameters, such as serum iron levels and transferrin saturation, will be recorded for analysis.

Indications for renal replacement therapy (RRT) will include:

- Fluid overload refractory to diuretics
- Severe hyperkalemia
- Severe metabolic acidosis
- Uremic manifestations such as encephalopathy, pericarditis, or seizures

The study will be submitted to the Institutional Review Board (IRB) of the Hospital Civil de Guadalajara “Fray Antonio Alcalde” and registered at ClinicalTrials.gov with the corresponding registration number.

This research will adhere to the ethical principles outlined in the Declaration of Helsinki and will be designed in accordance with CONSORT (Consolidated Standards of Reporting Trials) guidelines.

#### Statistical Analysis

An intention-to-treat approach will be adopted, including all randomized participants who receive the intervention, for both primary and secondary outcomes.

Categorical variables will be expressed as counts and percentages (%) and compared using either the chi-square test or Fisher’s exact test, as appropriate.

Continuous variables will be reported as median values (IQR), since normal distribution is not expected according to the Shapiro–Wilk test; between-group comparisons will be performed using the Mann–Whitney U test.

A repeated-measures analysis of variance (ANOVA) will be used to compare variables over time between groups. A Kaplan–Meier survival curve will be plotted for both groups and compared using the log-rank test. Missing data will be imputed using the mean linear interpolation method.

All statistical tests will be two-tailed, and a p-value < 0.05 will be considered statistically significant.

The analyses and figures will be performed using MedCalc software (Version 22.0.21, Ostend, Belgium) and GraphPad Prism (Version 10.2.3, Boston, Massachusetts, USA).

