### Theoretical and Conceptual Framework

Infections are among the least studied consequences of AKI. Although kidney diseases are well-recognized risk factors for infections—and infections remain one of the leading causes of death among patients with renal disease—the underlying mechanisms of this secondary immunodeficiency remain poorly defined [Steiger S]. Regarding the bidirectional relationship between AKI and infections, the recently published NARA-AKI prospective study demonstrated that postoperative AKI in non-cardiac surgery was associated with increased hospitalizations due to infections [Tagawa M, Kellum JA]. Beyond AKI, patients with chronic kidney disease (CKD) are more vulnerable to infections and exhibit worse outcomes than cohorts without CKD [Xu H, Su G]. Interestingly, not only the progression from AKI to CKD but also the decline in eGFR—*independent* of baseline or post-AKI eGFR—was independently associated with infection risk.

Several mechanisms may explain this increased susceptibility to infection. The immune dysfunction of CKD—characterized by impaired innate and adaptive immunity, decreased clearance of proinflammatory cytokines, and even epigenetic modifications in hematopoietic stem cells—adds to the alterations seen in AKI, such as disrupted kidney-immune system crosstalk, changes in immune cell composition and function, and an exaggerated inflammatory response [LaFavers K, Syed-Ahmed M]. Nevertheless, the precise pathophysiology of the elevated infection risk in patients transitioning from AKI to CKD remains incompletely understood.

Finally, a retrospective cohort study (Griffin BR) showed that recovery from AKI was associated with a 4.5-fold increase in the likelihood of infection (OR 4.53 [95% CI, 2.43–8.45];  $p < 0.0001$ ) within 30 days after hospital discharge. Moreover, the association between AKI and subsequent infection remained significant at 31–60 days and 91–365 days post-discharge, but not during the 61–90-day interval.

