#### Sampling Method

Potential participants for this study will be identified during routine hospital rounds for patients with acute kidney injury (AKI) and through concurrent review of medical records to confirm eligibility. If a patient is deemed eligible, the principal investigator will contact them to explain the study and provide a participant information and consent form.

After discussion with the patient and family members, the nephrology staff will obtain written informed consent prior to any study-related evaluations.

The intervention drug will be trimethoprim–sulfamethoxazole 800/160 mg, administered under double-blind conditions. Blinding will be achieved by ensuring that participants do not witness preparation of the study medication, and by assigning unblinded study personnel—who will not participate in outcome assessments—to handle preparation and administration.

The placebo will consist of magnesium tablets, administered at the same frequency—one tablet every 48 hours for three months.

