#### Elimination Criteria

- Patients who partially or completely discontinue the prophylactic antibiotic before completing three months of treatment
- Patients rehospitalized for non-infectious causes within the first three months
- Patients who take a different dose of prophylactic antibiotic than prescribed

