#### Presentation of Information

- Table of demographic characteristics comparing the intervention and control groups
- Quantitative comparison table of reported infections
- Kaplan–Meier comparative survival curve between intervention and control groups

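### The analysis set called intention-to-treat is restricted to randomised patients who receive the intervention, so it is a treated (modified) set and drops never-starters

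*Protocol*

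**What the plan says.** The protocol's Statistical Analysis section defines one analysis set: "An intention-to-treat approach will be adopted, including all randomized participants who receive the intervention", and applies it "for both primary and secondary outcomes". Nothing elsewhere returns randomised but untreated patients to an analysis.

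Four other places bear on this sentence:

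- **Materials and Methods** describes a "phase 2, randomized, prospective, double-blind, investigator-initiated, parallel-group, placebo-controlled clinical trial". **Sampling Method** maintains the blind partly by "assigning unblinded study personnel—who will not participate in outcome assessments—to handle preparation and administration".
- **Operationalization of Variables** gives treatment as a "categorical variable with two levels: active treatment or placebo", so both arms receive something. **Presentation of Information**, however, plans a "Table of demographic characteristics comparing the intervention and control groups", where the word intervention means the active arm.
- The same list of variables includes infections by site, readmission for infection, septic shock and death among the primary outcomes.
- **Elimination Criteria** would remove further randomised patients, among them "Patients who partially or completely discontinue the prophylactic antibiotic before completing three months of treatment", as well as those readmitted for a reason other than infection and those who take a different dose.

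**The concern.** Intention-to-treat keeps every randomised patient in the arm allocated, so that the groups compared are the groups randomisation formed. A condition of receipt breaks that. A patient allocated but infected, readmitted or dead before the first tablet leaves the analysis, and the event that removed the patient may be one the trial sets out to count.

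A treated-only set is often defended on the ground that nobody who influences the first dose knows the arm. That defence is weaker here, because the staff who prepare and give the tablets are unblinded. Keeping them out of outcome assessment protects the recording of events. It does not protect entry to the analysis set.

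The wording is also ambiguous. If intervention means the active drug, as it does in Presentation of Information, the condition could be read as applying to one arm only.

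At stake is a result reported as intention-to-treat that lacks the property the name promises.

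**Working it through.** **1. Label against definition.** The label implies all randomised patients. The definition is randomised *and* received. The two differ by the never-starters. This step needs no figure, and it is the defect itself.

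**2. The protocol's own sample size.** Inputs from Sample Size: 59% v 29.5%, two-sided 5%, 90% power. With p̄ = (0.59 + 0.295)/2 = 0.4425 and d = 0.295:

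n = (1.960 + 1.282)² × 2 × 0.4425 × 0.5575 / 0.295² = 59.6, so 60 per group.

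The stated 60 is reproduced. The formula with pooled variance under the null and unpooled under the alternative gives 58, and the power at 60 per group is then 91.2%.

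**3. Possible bias under a true null.** Assumptions, none of them in the protocol: the true risk is 59% in both arms; a fraction f of the active arm never starts and is dropped; their infection risk is r; nobody is dropped from control.

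- Risk among active starters = (0.59 − f·r)/(1 − f).
- Spurious difference D = 0.59 − that risk.
- Type I error ≈ 1 − Φ(1.96 − D/SE) + Φ(−1.96 − D/SE), with 60 v 60(1 − f) patients.

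For f = 10% and r = 80%: (0.59 − 0.08)/0.90 = 0.567, D = 0.023, SE = 0.0926, D/SE = 0.25, type I error 5.7%.

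| f dropped, active arm only | r | D (points) | Type I error |
|---|---|---|---|
| any | 59% (average) | 0 | 5.0% |
| 10% | 80% | 2.3 | 5.7% |
| 10% | 100% | 4.6 | 7.8% |
| 20% | 80% | 5.3 | 8.5% |
| 20% | 100% | 10.3 | 18.5% |

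The same loss in control only would shift the difference against the drug.

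**4. Loss in both arms.** Take 35/60 infected in control and 18/60 in the active arm, a difference of 58.3% − 30.0% = 28.3 points. Drop three infected never-starters from each arm (assumed): 32/57 − 15/57 = 56.1% − 26.3% = 29.8 points. The difference moves by 1.5 points. The active-arm rate alone falls by 3.7 points (30.0% to 26.3%), but that is a shift in the treatment comparison only if control loses nobody.

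**5. Cost of keeping never-starters.** Assume that active-arm never-starters carry the control risk. The active-arm risk becomes p₂ = 0.295(1 − f) + 0.59f, and

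power = Φ{[d√n − 1.96√(2p̄(1 − p̄))] / √(p₁(1 − p₁) + p₂(1 − p₂))}, with p₁ = 0.59, d = p₁ − p₂ and p̄ their mean.

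At f = 10%: p₂ = 0.3245, d = 0.2655, p̄ = 0.457, n = 60, giving Φ[(2.057 − 1.381)/0.679] = Φ(0.995) = 84.0%.

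| Never-starters (assumed) | All 60 per arm analysed | Never-starters dropped, rates unchanged |
|---|---|---|
| 2% | 90.0% | 90.7% |
| 5% | 88.0% | 89.8% |
| 10% | 84.0% | 88.1% |
| 20% | 74.1% | 84.0% |

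**The case against.** The strongest reply is that the mismatch is one of wording and may have little effect. If few patients fail to start, or if those who fail are like the rest, the result hardly moves; losses of equal size in both arms shift the difference by only 1.5 points in the example. That stands as to size. It does not rescue the definition, which is the only one the protocol gives and covers every efficacy outcome. It is not a detail left for a later document.

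Three stronger readings are tempting, and the protocol does not support them.

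- *That unblinded staff decide who starts.* Sampling Method has them prepare and give the tablets as a blinding measure, and gives them no say over whether a patient begins. Dosing runs for three months in outpatients, so patients may well decide receipt themselves. Declining, readmission, infection and death are not staff decisions. What remains is an opportunity.
- *That the events lost fall in the period of highest risk.* Theoretical and Conceptual Framework cites an odds ratio of 4.53 "within 30 days after hospital discharge". For 31–60 and 91–365 days it reports significance without figures, and for 61–90 days no significant association. That does not show the first month to be the strongest window, and an odds ratio for AKI against no AKI is not an absolute rate over time. The interval from randomisation to first tablet is not stated either.
- *That the bias is 3.7 points in the drug's favour.* That needs three assumed never-starters, all infected and all in the active arm.

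**Conclusion.** The sentence is wrong as written: it names intention-to-treat and defines a treated set. That conclusion rests on the text alone. The single-arm reading of intervention is possible but not the natural one, since the treatment variable has two levels; it is a further reason to reword.

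The size of any bias cannot be taken from the protocol, because no never-starter rate is given. It is nil if everyone starts or if those dropped have average risk. It is about 2.3 to 4.6 points, with type I error of about 5.7% to 7.8%, on the assumption of a true null and 10% dropped from the active arm only at 80% to 100% risk. It grows with the fraction dropped and with imbalance between arms. The change should be made, but nothing shows that the trial's result will be materially biased.

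**What to change.** In Statistical Analysis, define the primary set along these lines: all randomised participants, analysed in the arm to which they were allocated, whether or not any study tablet was taken, with outcomes collected to day 90. A set limited to those who took at least one tablet of either kind can serve for adverse events and as a sensitivity analysis, under a name other than intention-to-treat.

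Elimination Criteria must be reconciled at the same time, so that its three rules do not remove randomised patients from this set. Otherwise the two sections would contradict each other: a patient readmitted for a non-infectious cause before the first tablet would be kept by one and removed by the other.

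The edit touches two sections. Its statistical price is dilution, modest at low never-starter rates (about 88% power at 5%, 84% at 10%) but not at 20% (74%), on the assumption that active-arm never-starters carry the control risk. Data collection relies on the institutional record, so infections treated outside the hospital may be missed in never-starters; direct contact up to day 90 would reduce that gap.

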### Background

Following an episode of AKI, infections are a frequent complication.

In a retrospective Spanish cohort, infection surveillance began three months after the AKI episode. Over a median follow-up of nine months (IQR 2–56), 153 patients (42%) developed at least one infection. The most common were urinary tract infections [67 (44%)], respiratory tract infections [46 (30%)], soft tissue infections [14 (9%)], and abdominal infections [14 (9%)]. No specific baseline variable was associated with infection type.

Factors linked to infection during follow-up were analyzed using Cox regression. In univariate analysis, the following were associated with infection risk: older age [HR 1.18 (95% CI, 1.05–1.33),  $P = 0.005$ ], cognitive impairment [HR 1.51 (95% CI, 1.00–2.28),  $P = 0.050$ ], lower eGFR three months post-AKI [HR 0.91 (95% CI, 0.86–0.97),  $P = 0.002$ ], decline in eGFR from baseline to three months [HR 1.07 (95% CI, 1.01–1.14),  $P = 0.028$ ], and transition from AKI to chronic kidney disease (CKD) [HR 1.55 (95% CI, 1.13–2.14),  $P = 0.007$ ].

Baseline eGFR differed significantly between patients who developed infection and those who did not ( $P = 0.038$ ), although the nadir and post-AKI eGFR values were similar between groups ( $P = 0.289$  and  $P = 0.215$ , respectively).

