### Sample Size

To determine, with a 95% confidence level and 90% statistical power, whether the proportion of 59% in sample A differs from 29.5% in sample B, a total of 60 individuals per group will be required.

This study aims to detect a clinically significant difference of 0.8 ( $Z\alpha/2 = 1.96$ ,  $Z\beta = 0.84$ ) with a standard deviation of 1.5. Sample size calculations are based on the assumption

that approximately 30% of patients with AKI will experience a subsequent infection.

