#### Inclusion Criteria

Patients with severe AKI and known baseline serum creatinine (SCr) levels—defined as the most recent SCr value within the six months preceding hospitalization—will be included. Participants must also have available serum creatinine data for the months following discharge to assess major adverse kidney events (MAKE) at 90 days post-AKI.

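### All planned infection comparisons are unadjusted, although age and pre-admission kidney function will be known for every patient; adjusting is a small, nearly free gain, not the repair of an error

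*Protocol*

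**What the plan says.** The Statistical Analysis section of the protocol fixes the tests. Categorical variables, which include every infection outcome in Operationalization of Variables, are "compared using either the chi-square test" or Fisher's exact test. The Kaplan–Meier curves are compared by log-rank. No covariate-adjusted or stratified infection comparison appears anywhere in the protocol.

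The Background, describing a retrospective cohort, lists factors associated with infection in univariate Cox regression. Among them is "older age [HR 1.18 (95% CI, 1.05–1.33", P = 0.005. It adds separately: "Baseline eGFR differed significantly between patients who developed infection and those who did not" (P = 0.038, with no effect size or direction).

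Both variables will be held at entry. The Inclusion Criteria require "known baseline serum creatinine (SCr) levels" from the six months before admission, and the Exclusion Criteria set a lower age limit, so age must be recorded. Materials and Methods mentions sequences generated by stratum, but names no stratification factor, and the analysis uses none.

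**The concern.** Where baseline variables predict the outcome, an analysis that uses them estimates the treatment effect more precisely from the same patients. It also takes out whatever part of the observed difference comes from those variables falling unevenly between arms. With 60 per arm some unevenness is expected. The protocol cites two such variables, will hold both, and then fixes tests that use neither.

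Timing matters too. Presentation of Information plans a table comparing demographics between arms. If that table shows an imbalance in age or kidney function and no adjustment rule exists, any adjusted analysis would be chosen after seeing the data.

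**Working it through.** **1. The plan's own sample size.** Inputs from Sample Size and Statistical Analysis: "the proportion of 59% in sample A differs from 29.5% in sample B", "with a 95% confidence level and 90% statistical power", two-sided 5% ("All statistical tests will be two-tailed, and a p-value < 0.05 will be considered statistically significant"). Pooled formula:

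n = [1.96·√(2·0.4425·0.5575) + 1.2816·√(0.59·0.41 + 0.295·0.705)]² / 0.295² = (1.377 + 0.860)² / 0.0870 ≈ 57.5, so 58 per group.

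This agrees closely with "a total of 60 individuals per group will be required". Power at 60 per group is 91.2% by the pooled formula and 92.6% unpooled. The unpooled form is used below, so that adjusted and unadjusted results are comparable.

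**2. How prognostic the two variables are.** The Background gives no unit for age and no effect size for eGFR, but effects per SD can be inferred.

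- Age: ln(1.18) = 0.166; SE = (ln 1.33 − ln 1.05)/3.92 = 0.0603; z = 2.74. With 153 events, log HR per SD ≈ 2.74/√153 = 0.22 (HR about 1.25 per SD).
- Baseline eGFR: P = 0.038 gives z = 2.07. The cohort had 153/0.42 ≈ 364 patients, so about 211 without infection. Standardised difference ≈ 2.07·√(1/153 + 1/211) = 0.22.
- Combined, if independent: √(0.22² + 0.22²) = 0.31. Overlap between age and eGFR would lower this; moving from log HR to log odds would raise it. A range of 0.25 to 0.50 per SD is used.

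The cohort's remaining kidney-related factors (eGFR at three months, its decline, and AKI-to-CKD transition) arise after baseline and cannot be covariates.

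**3. Precision gained.** Take a standard normal prognostic score with logit slope b and intercepts set to give the stated marginal rates. With 1:1 allocation, the variance of the risk difference times n per arm is:

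- unadjusted: p_c(1−p_c) + p_t(1−p_t) = 0.2419 + 0.2080 = 0.4499;
- adjusted and standardised: E[p_c(x)(1−p_c(x))] + E[p_t(x)(1−p_t(x))] + Var[p_t(x)−p_c(x)]/2, evaluated numerically.

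Power = Φ(d/√(V/60) − 1.96). Unadjusted at the design rates: 0.295/√(0.4499/60) = 3.41, giving 92.6%.

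| Slope per SD | Variance cut, 59% v 29.5% | Unadjusted n per arm matching 60 adjusted | Power, 59% v 29.5% (unadjusted 92.6%) | Power, 30% v 15% (unadjusted 51.6%) |
|---|---|---|---|---|
| 0.25 | 1.4% | 60.8 | 92.9% | 52.0% |
| 0.35 | 2.6% | 61.6 | 93.2% | 52.4% |
| 0.50 | 5.0% | 63.2 | 93.8% | 53.2% |

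The 30% is the other infection rate given in Sample Size; halving it to 15% is an assumption.

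**4. Chance imbalance.** The standardised difference in a covariate between arms has SD √(2/60) = 0.18, so 95% of trials fall within ±1.96·0.18 = ±0.36 SD. The resulting shift in the risk difference is about b × 0.36 × the mean of p(1−p) over arms. At the design rates that mean is 0.4499/2 = 0.225:

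- b = 0.25: 0.25·0.36·0.225 ≈ 2.0 points;
- b = 0.50: 0.50·0.36·0.225 ≈ 4.0 points.

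This compares with a planned difference of 29.5 points. At 30% v 15% the mean is (0.21 + 0.1275)/2 = 0.169, so the shift is about 1.5 to 3.0 points on a 15-point difference.

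**5. Feasibility.** At the design rates about 60·0.59 + 60·0.295 ≈ 53 infected patients are expected, against three coefficients. At 30% v 15% it is 18 + 9 = 27, still workable for two covariates but not for many strata.

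**The case against.** The strongest reply is that nothing here is wrong. Chi-square and log-rank are valid primary tests in a randomised trial and match the basis of the sample size. Their 5% error already allows for chance imbalance. Covariate choice is often left to an SAP, and one may exist. All of that stands, and it sets the level of the point. The remaining argument is that this protocol does state its tests, so an adjusted analysis in an SAP would need the protocol to agree with it.

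A second reply is that the evidence is thin. The associations are univariate, baseline eGFR has only a P value, and the cohort counted infections from three months after AKI, whereas the trial counts them in the 90 days after discharge. That also stands: the size of the gain is inferred, not shown.

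A third is that the change is more than one sentence, because Operationalization of Variables lists infection sites separately and has no any-infection variable. That is correct, and the fix below includes the definition.

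A reader might infer something stronger: that the protocol names powerful predictors and discards substantial power. A combined slope of 1.0 per SD (AUC about 0.74) would indeed cut the variance by 16% and lift power from 92.6% to 96.0%. The documents do not support such a slope; their own figures give about 0.3. Nor do they support reading the unadjusted comparison as biased.

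**Conclusion.** The point holds as a minor improvement. The planned infection tests are valid but leave unused two baseline variables that the protocol associates with infection and will hold for everyone. The supported gain is a variance cut of about 1–5%, equal to roughly 1–3 patients per arm, 0.3–1.2 power points at 59% v 29.5%, or 0.4–1.6 points at an assumed 30% v 15%. Adjustment would also remove a shift of about 2–4 points at the 95% limit of chance imbalance under the design rates; typical shifts are smaller.

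This rests on an inferred slope of 0.25–0.50 per SD, a roughly normal score, and the cohort's associations carrying over to the first 90 days. If they do not carry over, there is essentially no gain, but the test also remains valid. Adjustment would not rescue power if the 30% rate is the right one for controls. That inconsistency within Sample Size is a separate and much larger matter.

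**What to change.** In Statistical Analysis, pre-specify the following:

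- Primary comparison: any infection by day 90 (yes/no), the composite implied by the Primary Objective, by logistic regression on treatment, age and pre-admission eGFR, the last two continuous. Include any stratification factor actually used in randomisation.
- Primary estimate: the standardised (marginal) risk difference with 95% CI, which stays on the scale of the sample-size calculation.
- Time to first infection: a Cox model with the same covariates.
- Unadjusted sensitivity analyses: the present chi-square or Fisher's exact test and the log-rank test.

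Two supporting edits are needed. Add the any-infection variable to Operationalization of Variables, and name there the equation that turns pre-admission creatinine into eGFR. Name the stratification factors, if any, in Materials and Methods.

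The cost is a few sentences, with no new data and no extra patients. The team should confirm that the listed software produces the standardised risk difference with its interval, or add a package that does. The change should be made before any outcome data are seen by arm.
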